**Figure 2. Participant recruitment aged 16 or over (NZ) or 18 or over (AU)**

### 8.3.2 Recruitment of eligible participants *under* the age of 16 (NZ) or 18 (AU)

When the rooms or clinic is made aware that a minor will be presenting for consultation to discuss surgical bariatric treatment options, the rooms or clinic should contact the Registry to request a consent form in order to potentially recruit the minor patient. The Registry will immediately email the consent forms with instructions. This will ensure that the consent forms are on hand for the patient's appointment.

Consenting a minor to participate in the Registry will follow the Australian Paediatric Research Ethics & Governance Network Guide (2017). Surgeons, gastroenterologists or hospital clinic staff are to discuss the Registry with the minor patients and their parent(s)/legal guardian(s) and give both the patient and parent(s)/guardian(s) a Registry flyer. The rooms or clinic should also have a Registry poster displayed. Further, the Parent(s)/Legal Guardian(s) Informed Consent Form (ICF) will be provided to the parent(s)/legal guardian(s) and the clinician, as an investigator in the study, is to determine the

capacity of the minor participant to understand the research. If the clinician investigator determines that the minor does not have capacity to consent, he/she is to provide information about what their participation will involve in language they understand, using the Information Sheet for Minors. The determination of capacity is to be documented by the clinician in the medical record and a study note should be provided to the Registry.

To protect from the perception of coercion to participate, the consent process should be carried out by a member of staff/the clinic who is not directly involved in the minor's care. The member of staff will verbally go over the consent form in its entirety with the minor and their parent(s)/guardian(s). The staff must clearly state that participation in the Registry is voluntary; that consent can be withdrawn at any time; and that their decision whether or not to participate will not affect the quality of the treatment they will receive. Further, prior to the individual giving consent, the opportunity must be given to consult with another health professional, family member or member of their community.

The form should only be signed when the staff member has been given surety that it is understood by the individual. Three copies of the form are required to be signed by the person giving consent, the person who carried out the consent process and a witness. One copy will be given to the person who gave consent, one is to be kept in the patient's medical record (an electronic copy can be made), and a copy is required to be sent to the Registry. If the consent process is taking place in a hospital clinic, the entire copy of the ICF should be sent to the hospital's Health Information Services (HIS) to be entered in the patient's medical record.

If the minor is mature enough to understand and capable of consenting to participation, they should also be given their own ICF to sign or they can countersign Parent(s)/Legal Guardian(s) ICF. This needs to be witnessed by clinic or room staff who are present at the time of the consent or the patient's parent/guardian. One copy will be given to the patient, one is to be kept in the patient's medical record (an electronic copy can be made), and a copy is required to be sent to the Registry. If the consent process is taking place in a hospital clinic, the entire copy of the ICF should be sent to the hospital's Health Information Services (HIS) to be entered in the patient's medical record.

The Registry will keep a log which will verify that consent was carried out for each minor participant. The log will state: the date(s) when the consent form was requested and sent; the date of consent; and the date the Registry received the signed copy of the consent form. All Registry copies of the consent forms will be securely filed and stored within the Registry.

No minors' data will be held within the Registry prior to receiving a signed consent form.

Consent for participation of the minor can be withdrawn at any time. The 'Form for Withdrawal of Participation-Parent/Guardian' must be completed. Three copies of the form must be signed with one copy given to the parent/guardian, one for the participant's medical record and one provided to the Registry. The Registry will complete the withdrawal in the Consent Log. Once consent has been withdrawn, all health information relating to the participant will be deleted from the database.

#### ***8.3.2.1 Re-negotiating consent when a minor participant reaches 16 years (NZ) or 18 years (AU)***

As part of the Registry's validation processes, it will routinely check the age of Registry participants. The process of doing this routinely will alert the Registry to any 16 year old New Zealand or 18 year old Australian participants. When a 16 year old (NZ) or 18-year-old (AU) participant is identified by the Registry, Registry staff will review the Consent Log to determine who gave consent for treatment. If consent was given by a parent or guardian at the time of the patient being a minor, the participant will be posted a specific Participant Fact Sheet 'Participant Fact Sheet for 16+ (NZ)' or '...18+ (AU)', allowing the opportunity to consider whether or not to continue their participation.

This PFS explains the purpose of the Bariatric Surgery Registry and that they had previously been enrolled at the time of their operation when they were younger. It explains how the reason why they were enrolled and what their continued participation would involve. It also advises that their participation is voluntary and how to opt out if they wish to cease their involvement. General contact information is listed along with details about making a complaint to the relevant ethics committee and a free call number (0 800 in New Zealand or 1 800 in Australia) is also provided. If no contact with the Registry is made within 14 days of posting the PFS, it will be presumed that the participant agrees to their continued participation. All participants are able to opt out at any time.

### **8.3.3 Waiver of consent**

A waiver of consent is required to allow for the opt out approach; for the deceased: for people highly dependent on medical care (in particular instances, only); and for data linkages (including with electronic medical records).

#### **8.3.3.1 Waiver of consent while completing opt out approach**

Patients' data is held prior to the completion of the opt out approach (which includes the mailing of the PFS) twice during the data acquisition process:

- from the time bariatric patient information is submitted to the Registry until the two weeks since posting the PFS has passed; and
- from the time when the Registry receives the discharge coding (ICD-10-AM reports) for bariatric patients whose data was not previously submitted until two weeks since posting the PFS has passed.

The Monash University Office of General Counsel considered this process to be acceptable under the *Privacy Act of 1988* (2014). The Registry's data acquisition process has had prior review and approval from the ethics committees in Australia and New Zealand listed in **section 2**. The lead ethics committee for the Bariatric Surgery Registry, the Alfred Hospital Human Research Ethics Committee, considered that this process is preferable to the surgeon obtaining direct informed consent at the time of consultation, which holds a risk of power imbalance, coercion and difficult to document that the process had occurred. Ethical considerations are discussed more completely in **section 9**.

#### **8.3.3.2 Waiver of consent for the deceased**

A waiver of consent for the deceased is required in the event that the patient dies following bariatric surgery so as not to burden next of kin. Information related to mortality is essential to determine if the cause of death was related to the bariatric surgery. The Alfred Hospital HREC (Australia), the New Zealand HDEC and all other approving HRECs in **Tables 3** and **4** considered this waiver and approved its use. Having a waiver of consent for this instance implies that the deceased did not need to give previous consent to request or hold their information, nor is consent required from their next of kin to hold the data of the deceased.

#### **8.3.3.3 Waiver of consent for people highly dependent on medical care**

Bariatric patients may become unconscious, receive intensive care, emergency care or end-of-life care as a consequence of having their surgical procedure(s). Information about adverse events leading to patients receiving this type of care or to be in this condition are critically vital to demonstrate the safety and quality of bariatric surgery.

The surgeon, gastroenterologist or hospital should advise the patient's parent, guardian, or other authorised representative of the patient's inclusion in the study and allow them to consider whether their inclusion would be contrary to the patient's interests. However, if no other authority is acting on behalf of the patient, a waiver of consent is required. If such a patient regains capacity for consent, they should be advised as soon as reasonable possible of their inclusion in the Registry and be provided with opportunity to opt out.

#### **8.3.3.4 Waiver of consent for linkage with participants' electronic medical record (EMR)**

Data can be collected directly from a participant's medical record held on the medical practice

software (an electronic medical record or “EMR”) of their surgeon/gastroenterologist/hospital. (Refer to section **8.4.2.1**). In order to link with the software, the Registry needs to disclose participant information to the software provider for the purpose of locating the participant in the medical record. All information disclosed to the software contractor for this purpose is to be deleted after the linkage is completed.

A waiver of consent is needed for the Registry’s disclosure to the software provider to carry out the data linkage.

#### **8.3.3.5 Waiver of consent with data linkages**

The Registry intends to link with other repositories of health information as a means of validating its data as described in **section 8.4.2.4**. Health information about individual participants may be collected who have not completed the opt out approach, just as it may be with the hospital ICD-10-AM reports.

This protocol adheres to the *National Statement for Ethical Conduct in Human Research 2007* (2018) and with New Zealand’s *Ethical Guidelines for Observational Studies: Observational Research, Audits and Related Activities* (2012). Section 6.47 of the NZ guidelines states, “In the case of audits and related activities it may be ethical to use health information without additional or specific consent, as these activities are sometimes an essential part of high-quality health care delivery, so the activity may be one of the reasons why the data were collected”.

## **8.4 Data**

### **8.4.1 Data collection stages**

#### **i. Operation data collection**

Data is collected about bariatric patients and their procedures after the surgery has taken place.

[figure not shown]
#### **ii. Perioperative follow-up data**

Follow-up data is collected peri-operatively, with regard to the first 90 days after the surgery for all participants. The Registry will not accept routine follow-up data captured prior to 20 days after the surgery. See **Figure 3**.

#### **iii. Annual follow-up data collection**

Follow-up data is collected on an annual basis for primary bariatric procedures only. Acceptable data collecting periods are from 3 months prior to the anniversary of the surgery to 3 months following the anniversary. See **Figure 3**.

Figure 3. Follow up data collection

## 8.4.2 Data collection processes

### 8.4.2.1 Data collected from surgeons, gastroenterologists, and hospital data collectors

The health professionals who performed the procedures (surgeons or gastroenterologists) have the overarching responsibility for submitting data. However, they can delegate submission to their practice staff or hospital data collectors. Data is provided to the Registry:

- in Australia, using:
  - the web browser with secure authorised entry using the Bariatric Surgery Registry Interface (BSR-*i*);
  - paper based data forms securely faxed or posted; or
  - secure electronic record transfer from surgeons' or hospitals' electronic medical record (EMR)
- in New Zealand, using:
  - the web browser with secure authorised entry using the Bariatric Surgery Registry Interface (BSR-*i*); or
  - secure electronic record transfer from surgeons' or hospitals' electronic medical record.

Practitioners who choose to have data collected from their EMR will sign an agreement with their contracted provider to have their patients' records accessed for the purpose of data collection. The Registry would provide an encrypted CSV file on the secure file transfer platform (SFTP) to the software provider. Once the software provider carries out the linkage, the data would be encrypted, converted to an agreed file format, and uploaded to the Monash University SFTP for Registry staff to access.

### 8.4.2.2 Data collected from ICD-10-AM coding reports (or similar hospital discharge reports)

Hospital Information Services (HIS) at each hospital site, or of a private hospital group, are to provide regular ICD-10-AM coding reports (or similar discharge reports) for bariatric procedures performed by surgeons or gastroenterologists who participate in the Registry. The coding reports include patient demographic and procedure information. In Australia, these reports are sent to the Registry using a secure file transfer platform (SFTP). In New Zealand, these reports are sent to UniServices in accordance with the agreed Memorandum of Understanding for each site.

The ICD-10-AM coding (or similar) reports provided by HIS are used to verify data submitted to the Registry. The reports confirm the procedures already submitted and allow Registry staff to identify those which have not. Surgeons, gastroenterologists and hospital data collectors will be asked to provide the remaining clinical information for the patients whose procedures were identified in the coding report:

- device/stapling information;
- whether the operation was a primary or revision;
- height/weight information;
- diabetes status and treatment; and
- perioperative follow-up data is also requested for efficiency.

Patients whose details are obtained from these reports are sent a PFS and the opt-out approach is followed according to the process described in section 8.3. Once the opt out period has passed, if the request for the missing data elements from the surgeon or gastroenterologist was not met, Registry staff will contact the participant to collect the required information.

#### **8.4.2.3 Data collected from participants**

##### **A. Self-reported clinical and follow up data**

When surgeons, gastroenterologists or public data collectors indicate they have not seen the participant and cannot report follow-up, the Registry staff will contact the participant for a brief phone call (using the Call Protocols) to collect the follow-up information related to the perioperative period and/or 12 month interval after surgery. (See **Figure 4**).

If the participant is a minor, the Registry staff member must check the Consent Log to determine if the minor had consented, or a parent/guardian did on their behalf. Registry staff will then speak directly with the individual who provided consent as per the consent form.

Participants (or parent/guardian) may also be asked for any missing data elements about their procedure not previously collected.

As explained in the PFS, participants do not have to agree to this contact but still keep their information on the Registry (partial opt out).

If a participant is to be followed up by the Registry, five attempts will be made to contact the participant before they are allocated to “Lost to Follow-Up”. All information about the participants lost to follow-up status is held by the Registry, as they have been through the opt out approach. These individuals may be captured again if they undergo further bariatric surgery.

An SMS/Secure Portal platform will be developed as another method to obtain follow-up data from Registry participants, through SMS, email and web based links. This platform will invite participants to link to a secure portal at various stages of their post-operative experience. If they do not respond to the request for follow-up, the Registry will call the participants. The SMS/Secure Portal platform will be designed to engage with participants by providing useful information during their post-surgery experience and allow them to give their own data back to the Registry.

##### **B. Participant feedback and quality assurance**

For quality assurance purposes and as a basis for the development of the SMS/Secure Portal platform as described above, participants will be given the opportunity to provide feedback on their experience with the Registry and offer how the Registry could better support their journey as bariatric patients. This feedback may take place during follow-up phone calls made by the Registry’s call centre staff or via an online form on the Bariatric Surgery Registry website that is currently under construction.

[figure not shown]
#### **8.4.2.4 Data collected from linkages with other repositories of health information**

Data may be collected with linkages to other repositories, or datasets, of health information for the purpose of verifying critical quality data as explained in the **section 8.4.4**. Any request to link with a data linkage unit will require the necessary ethic approvals.

#### ***8.4.2.5 Data Collected by other interested parties***

More comprehensive data can potentially be collected by interested sub-groups but approval from the Bariatric Surgery Registry Steering Committee and the lead ethics committee, the Alfred Hospital Human Research Ethics Committee, is required.

Figure 4. Follow-up data collection scheme.

### 8.4.3 Data elements

Data elements are defined in the Registry's data dictionary and governed by the Steering Committee, with any changes managed through a data element variation process.

The data elements collected include:

- **Patient data elements:**

*Patient Identifiers:*

- full name;
- address;
- date of birth;
- UR number/hospital (and IHI numbers when available); and
- email address (if supplied by patient)

- **Patient demographic information:**

- Medicare number (Australia only)
- Department of Veterans Affairs (DVA) number;
- NHI number (New Zealand only);
- phone numbers;
- gender; and
- indigenous status (Australia)/ethnicity (New Zealand)

- **Operation data elements:**

*Clinical details:*

- start weight (for primary participants only);
- day-of-surgery (DOS) weight;
- height;
- diabetes status and treatment; and
- concurrent renal and liver transplant

*Procedural information:*

- surgeon name;
- procedure date;
- procedure type;
- surgical approach used (open, laparoscopic, robotic)
- primary/ revision;
- planned or unplanned revision status;
- reason for revision;
- bariatric procedure prior to revision;
- if the procedure was abandoned;
- reason for abandoning procedure;
- length of hospital stay; and
- mortality status including date of death and whether the death was likely to be related to the bariatric procedure

*Device or Staple details:*

- type;
- brand;
- model;
- port fixation method; and
- buttress

- **Follow-up data elements**

*Elements for Perioperative (up to 90 days post-surgery) Data:*

- date participant had a post-operative review
- occurrence of unplanned return to theatre and reason/ complication occurrence of unplanned admission to intensive care and reason/ complication;
- occurrence of unplanned re-admission to hospital and reason/ complication;
- prolonged hospital stay and reason/ complication; and,

- mortality status including date of death and whether the death was likely to be related to the bariatric procedure

*Elements for Subsequent Clinical Data of Primary Participants (collected annually for ten years):*

- weight;
- diabetes status and treatment;
- re-operation and reason; and
- mortality status including date of death and whether the death was likely to be related to the bariatric procedure

#### 8.4.4 Data quality

Data completeness and accuracy are optimised through routine in-built validation and completion checks in the Registry database to minimize data entry error. These include:

- data entry controlled by form logic and limited to feasible data;
- use of built in edit checks to ensure data meets the required formats and range;
- accuracy enhanced by the use of exhaustive drop down lists providing all possible answers to minimize free text entry where applicable;
- use of hide and show mechanisms to guide data entry to required fields;
- use of explanatory texts to assist data entry;
- validation rules applied at the time of submission with alerts to assist with errors and missing data; and,
- the use of a participant management system to list incomplete data and other actions required.

Additional quality checks post data entry includes checking for:

- duplicate data;
- missing data;
- data consistency; and
- data validity.

Data quality and completeness are checked at a number of stages of the data management process. Errors in data quality, when identified, may be referred back to contributing surgeons, gastroenterologists or hospitals for review.

Case ascertainment, as well as both brief and comprehensive audit processes, are performed on site by Monash University Registry staff (Australia only). Registry staff perform regular remote audit checks to verify the accuracy of data received from surgeons and gastroenterologists. This is done during the course of a follow-up phone call from the call centre or by Registry staff directly contacting surgeons' or gastroenterologists' rooms.

Completeness and accuracy of the eligible population captured by the Registry is assessed using hospital ICD-10-AM coding reports (or similar hospital discharge reports) provided by participating hospitals or hospital groups. Cross-checking with these reports allows for complete data capture at each hospital site and provides data validation for each procedure submitted by the surgeon or gastroenterologist. These reports are provided at regular intervals by the organisation's administrator and only contain data of participating surgeons and gastroenterologists.

In Australia, periodic linkages are intended with other repositories, or datasets, of health information that can validate Registry data. The ICD-10-AM discharge report validations and other data linkages will ensure that all eligible patients are included in the Registry and minimise the risk of bias in data entry by contributing surgeons and gastroenterologists. The linkages will also verify critical quality data such as patient mortality, defined adverse events and other outcome measures are completely captured. Requests to link New Zealand Registry data to national data sets will be considered by the Steering Committee on a case-by-case basis. For data linkages in Australia and New Zealand, the necessary approvals from an HREC/HDEC will be sought when required. Examples of repositories, their role in data validation, and what information will be collected and disclosed by the Registry are described in **Table 5**.

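### Section 8.4.4 claims complete capture at each site and inclusion of all eligible patients, but its coding reports cover only participating clinicians and no other mechanism secures the rest

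*Protocol*

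**What the plan says.** Section 8.4.4 makes three statements about completeness.

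- On assessment: "Completeness and accuracy of the eligible population captured by the Registry is assessed using hospital ICD-10-AM coding reports", supplied by participating hospitals or hospital groups.
- On sites: "Cross-checking with these reports allows for complete data capture at each hospital site".
- On the population: "The ICD-10-AM discharge report validations and other data linkages will ensure that all eligible patients are included in the Registry".

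The same section states that the reports "only contain data of participating surgeons and gastroenterologists". Section 8.4.2.2 sets the same limit: the reports are "for bariatric procedures performed by surgeons or gastroenterologists who participate in the Registry".

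The target population is wider. Section 8.1 makes anyone who has bariatric surgery for obesity in Australia or New Zealand eligible. Section 8.0 aims at the entire population, invites clinicians known to do this surgery, and says that their participation is voluntary. Section 3.1 sets an aim of 95% of the 27,000 surgeries (2017 figure) done each year in both countries.

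On other data sources, Section 8.4.4 says "In Australia, periodic linkages are intended with other repositories, or datasets, of health information". For New Zealand it says "Requests to link New Zealand Registry data to national data sets will be considered by the Steering Committee on a case-by-case basis".

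**The concern.** A file filtered to participating clinicians is silent about everyone else. If a non-participating surgeon operates at a participating hospital, the cross-check for that hospital can be clean while that surgeon's cases are missing. A hospital that sends no reports does not appear at all. The site-level and population-level statements in 8.4.4 therefore describe a property that the stated data source does not have.

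This matters because the Registry presents itself as a source of population-level data (Section 4.0), and Section 9 argues that registries need near-total capture for reliable reporting. A reader of 8.4.4 could take a good result from the report check as evidence that the eligible population is covered. If patients of non-participating clinicians differed in outcome from those captured, nothing in the check would reveal it.

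**Working it through.** **Step 1. Scope of the claims against scope of the data (all from the Protocol).**

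| Item | Scope | Section |
|---|---|---|
| Eligible population | Anyone having bariatric surgery for obesity, either country | 8.1 |
| Clinician participation | Voluntary | 8.0 |
| Coding reports | Participating clinicians at participating hospitals | 8.4.2.2, 8.4.4 |
| Site claim | Complete capture at each site | 8.4.4 |
| Population claim | All eligible patients, reports plus linkages | 8.4.4 |

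The third row is narrower than both claims. Within their scope the reports do useful work: unsubmitted procedures of participating clinicians are found and those patients enter recruitment (8.3, 8.4.2.2).

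**Step 2. Could another mechanism close the gap?**

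- *Adding sites and inviting known clinicians (2.0, 8.0).* This widens coverage but does not measure it.
- *On-site case ascertainment (8.4.4).* Australia only; its reach is not stated.
- *Record access for case ascertainment (8.4.5).* No country limit, but not said to reach non-participating clinicians.
- *Linkages (8.4.4, Table 5).* Intended in Australia and case by case in New Zealand. The insurer source is at present one insurer, and the State and Territory sets need application and ethics approval. Section 8.3.3.5 would allow information on people who have not completed opt-out, so missed cases could in principle surface. However, Table 5 describes both the insurer and the State and Territory sets as following people already in the Registry. Among the Table 5 examples, only the hospital coding extract has the stated role of finding omitted procedures, and that is the filtered source.

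**Step 3. What the 95% aim tolerates.**

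The plan's own figures: Section 3.2 gives over 26,000 Australian procedures (2017) and 889 in New Zealand (year ending 2014). Their sum is 26,000 + 889 = 26,889, in line with the rounded 27,000. The aim is 0.95 × 27,000 = 25,650.

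Let *s* be the share of procedures by participating clinicians at participating hospitals, *r* the share retained after full opt-out, and *l* the share of outside procedures recovered by linkage. Assume that every procedure inside the reports is submitted or recovered. Then

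capture = r × (s + (1 − s) × l).

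Section 10 puts the opt-out rate below 4%, so r = 96% is taken as the lower edge, treating that rate as full opt-out. The protocol gives neither *s* nor *l*; the values below are assumptions.

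| s | r = 100%, l = 0 | r = 96%, l = 0 |
|---|---|---|
| 100% | 100.0% | 96.0% |
| 95% | 95.0% | 91.2% |
| 90% | 90.0% | 86.4% |
| 80% | 80.0% | 76.8% |

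With l = 100%, every row returns to 100.0% or 96.0%.

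With l = 0, the aim needs s ≥ 0.95 / r, so the largest number outside the reports is 27,000 × (1 − 0.95 / r), rounded down:

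- r = 100%: s ≥ 95.0%; 1,350 procedures.
- r = 98% (assumed): s ≥ 96.9%; 826.5, so 826.
- r = 96%: s ≥ 99.0%; 281.25, so 281. Check: 0.96 × (27,000 − 281) = 25,650.2, which meets 25,650; with 282 outside it is 25,649.3, which does not.

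**The case against.** The strongest reply is that the limit is disclosed in the paragraph that makes the claim. The first statement in 8.4.4 concerns the population already captured and names participating hospitals, so it is fairly read as limited. That stands, and the point does not rest on that sentence. It does not rescue the site statement, or the population statement, which carries no such limit.

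Second, the population statement credits reports and linkages jointly. That is true, but an assurance of inclusion cannot rest on linkages that are conditional and mostly described for another purpose.

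Third, a reader might infer that the protocol judges its 95% aim by the report check. It does not say so: Section 3.1 sets the aim against an overall annual count, and 8.4.4 defines no score.

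Fourth, a reader might infer that the report check would always look perfect. That does not follow. Under 8.3.1, people who opt out and ask that no details be kept, and patients deleted after unresolved returned mail, leave nothing to match and can appear as omitted.

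Fifth, the shares in the table are assumed, so they illustrate tolerance and are no evidence of loss. That stands. Detailed numerator rules and code sets may properly sit in an analysis plan or the data dictionary, and their absence is not criticised here.

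**Conclusion.** The point holds as an overstatement in Section 8.4.4 of what its completeness mechanisms deliver. The reports support a claim about participating clinicians' procedures at participating hospitals. They do not support complete capture at every site or inclusion of all eligible patients, and the other mechanisms do not secure those properties as written.

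Its size is unknown. A reader might infer that the Registry misses a material share of procedures, or falls below the 90% participation level mentioned in Section 9. Neither is supported: the participating share is not given, and the 90% figure is part of the argument for opt-out, not an acceptance criterion. What can be said is that the margin is narrow: at most 1,350 of 27,000 procedures outside the reports with no opt-out loss, and 281 with a 4% loss, both assuming no recovery by linkage. If opt-outs count as collected, which Section 3.1 does not say, 1,350 applies throughout. Returned-mail deletions would tighten the margin by an amount that cannot be quantified from the protocol. No outcome definition or risk adjustment is shown to change; what changes is the conclusion that can be drawn about population coverage.

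**What to change.** 1. In Section 8.4.4, limit the site statement to complete capture of participating clinicians' procedures at each participating hospital.
2. In the same section, replace the assurance that all eligible patients are included. Say that the reports verify and recover participating clinicians' procedures at participating hospitals, and that other linkages, where approved, may identify further eligible procedures. Keep the remark on bias in data entry.
3. Judge the 95% aim of Section 3.1 against an external count of procedures by all providers for the same period, reported separately from report-based submission completeness. Where no such count exists, state capture as not known. The Section 3.2 figures show the type of source but mix years and should not be used unchanged.

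The cost is two wording changes and one ratio for each period and country where a count can be obtained; no new patient data are needed. The coverage statement becomes less favourable, and the external count will carry coding and timing differences. The protocol shows no annual New Zealand source, so one would have to be found.
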